- Body weight will be measured using digital electronic or beam balance scale to the nearest 0.1 kg. Prior to weight measurements, the scale should be set to zero to avoid drift in equipment functioning. Subjects will be weighed in examination gowns or in lightweight clothing and without shoes. If possible, weight measurements should be taken at the same time of day after the bladder is emptied so subjects are always evaluated in the same physiologic state.
- Tanner staging of subjects of age 8 years and above will be conducted by a qualified pediatric endocrinologist or by a physician trained in the method.²⁷

Any abnormalities present at baseline, or subsequent changes, will be documented in the appropriate sections of the eCRF. Any clinically significant abnormalities persisting at the end of the study will be followed by the investigator until resolution or until reaching a clinically stable endpoint.

Neurologic Examination

Neurologic examinations (including mental status, cranial nerves, motor examination [muscle tone, strength, deep tendon reflexes], cerebellar functions, and gait) will be performed by the investigators at all visits except Month 2.

Any abnormalities present at baseline, or subsequent changes from baseline, will be documented in the appropriate sections of the eCRF. Any clinically significant abnormalities persisting at the end of the study will be followed by the investigator until resolution or until reaching a clinically stable endpoint.

Bone Mineralization

Monitoring changes in bone mineralization will include: DEXA scans of the posterior-anterior lumbar spine (L1-L4) and total body less head area BMD and bone mineral content (BMC), and serum biochemical parameters of bone metabolism, including serum levels of alkaline phosphatase, calcium, phosphorus, parathyroid hormone (intact), 25-hydroxy-vitamin D, 1,25-dihydroxy-vitamin D, and IGF-1. Biochemical assessments will be obtained at screening, Month 6, and Month 12/early withdrawal. DEXA scans (without sedation) will be obtained at baseline, Month 6, and Month 12/early withdrawal. For all scans, up to 3 DEXA scan attempts will be performed all on the same day with the goal of obtaining 2 complete, movement-free scans, recognizing that it might not be possible to obtain 2 adequate scans in some younger children.

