10.2. Withdrawal From the Study

A subject will be withdrawn from the study for any of the following reasons:

- Lost to follow-up
- Withdrawal of consent
- The investigator or sponsor believes (eg, that for safety or tolerability reasons such as an adverse event) it is in the best interest of the subject to discontinue treatment.
- Death
- Other reasons
- If a female subject becomes pregnant during the study, she must be discontinued from the study and the pregnancy followed to term, if applicable.

During the study, subjects will also be withdrawn if:

- Subject develops status epilepticus not controlled by a single rescue agent.
- At the discretion of the investigator, subject develops any new seizure types or any clinically relevant safety issue.
- Subject requires greater than a 10-day course of medications that may impact bone metabolism, including intravenous or oral steroids, furosemide, growth hormone, NSAIDs, antacids, or calcium/vitamin D supplements.
- Subject develops nephrocalcinosis (diagnosed in any way) or develops a significant clinical adverse event (eg, serious event, treatment-limiting event, or other consideration) diagnosed as being related to a new kidney stone. Ultrasound results that suggest an asymptomatic kidney stone will not necessarily serve as a reason for withdrawal from the study.
- The investigator believes the subject to be at significant risk of suicidal or violent behavior.

If a subject discontinues treatment before the end of the open-label treatment phase, the end-of-study assessments should be obtained.

If a subject is lost to follow-up, every reasonable effort must be made by the study site personnel to contact the subject and determine the reason for discontinuation/withdrawal. The measures taken to follow-up must be documented.

When a subject withdraws before completing the study, the reason for withdrawal is to be documented in the CRF and in the source document. Study drug assigned to the withdrawn subject may not be assigned to another subject. Subjects who withdraw will not be replaced.

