11.2. Sample Size Determination

A total of 282 randomized subjects, 141 in each treatment group, will be recruited to the study. The sample size takes into account a 1-year dropout rate of 29%, which is a conservative estimate based on the dropout rates observed in a previous monotherapy study in the 6- to 15-year-old age group, Study TOPMAT-EPMN-106, including a dropout rate of 22% in the study overall (both double-blind and open-label phases) and a dropout rate of 35% for the double-blind phase. The sample size was estimated in order to achieve a sufficient precision for the estimates of the treatment effect on the key endpoints. The precision of the confidence interval (CI) estimates for the key safety parameters are shown below:

- *Annual change in BMD (L1-L4) Z-score:* In the Bone Mineral Density in Childhood Study (BMDCS), mean annual change in BMD (L1-L4) Z-score in 6- to 15-year-old healthy subjects was, as expected, minimal (0.01-0.07).³⁵ The standard deviation (SD) varied from 0.3 to 0.48 across sex and age groups.³⁵ Assuming an SD of 0.4, with 100 completed subjects per group, the 95% CI for the treatment difference will have a precision of 0.12.
- *Annual change in height Z-score in the 2- to 9-year-old age group:* In the monotherapy epilepsy study TOPMAT-EPMN-106, the observed change from baseline in mean height Z-score at 1 year among the 2- to 9-year-old subjects treated with topiramate 400 mg/day was -0.18, with an SD of 0.28.⁴⁰ Assuming that 53% of the subjects will be recruited in the 2- to 9-year-old age group, ie, 53 completed subjects per treatment group, the 95% CI for the treatment difference will have a precision of 0.11.
- *Incidence of kidney stone formation:* In the studies TOPMAT-PEP-3001 and TOPMAT-PEP-1002 in infants (1 month to 2 years of age), a 7% incidence of kidney stones was observed during the 1-year topiramate adjunctive treatment period.^{11,38} A sample size of 100 completed subjects per treatment group will provide a 95% CI (Wilson score CI) for the

treatment difference with a width of 0.12, assuming that the incidence of kidney stone formation is 7% and near zero in the topiramate group and the levetiracetam group, respectively.

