A 1-year study duration is justified based on the following:

- The American Academy Pediatrics Clinical Report Bone Densitometry in children and adolescents states that the recommended interval between repeat DEXA scans depends on progression of bone disorder, with a minimal interval between scans of 6 months, but often 1 year or more may be appropriate to allow measurable change to occur.³ The Position

statement on DEXA scans in children and adolescents from ISCD states that in pediatric patients, repeat scans should generally be obtained within 1 to 2 years for clinical purposes and in some settings, such as a patient in a research study and/or receiving a therapeutic skeletal agent, every 6 months.¹⁸ The shorter 6-month interval may reveal trends in skeletal losses and gains, reflecting variations in bone turnover from either a chronic disease or intervention, but ones not yet clinically significant. The ISCD suggests a minimum monitoring time interval of 6 months for repeating BMD measurement.⁴

- Abnormalities in height have been detected during 1 year of treatment in children treated with topiramate monotherapy. Topiramate as monotherapy for newly or recently diagnosed POS has been evaluated in 3 double-blind Phase 3 studies, each of which included subjects between the ages of 6 and 15 years of age at enrollment.³³ One of these 3 studies included post-baseline height or BMI data and also included an open-label extension phase.⁹ During the combined double-blind and open-label extension, there was a small percentage of children who met height criteria for growth delay.
- Renal stones as documented by renal ultrasound have been demonstrated within a 1-year treatment duration with topiramate. Results from the open-label extension study performed in 284 infants with epilepsy 1 to 24 months of age treated with topiramate for 1 year showed that 18 of 284 subjects (6.3%) had nephrolithiasis detected by sonogram approximately 4 to 5 months into the study.¹¹

Additional ethical concerns relate to consent/assent and ensuring that ethical principles related to pediatric subjects as vulnerable subjects are in effect, primarily to ensure that total allowable blood volumes are not exceeded during study conduct.

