5	Month 3	76 to 135	90
6	Month 6	136 to 225	180
7	Month 9	226 to 315	270
8	Month 12	>=316	360

^a The randomization day is Day 1.

The analysis windows for DEXA is given in [Table 8](#).

Table 8: Definition of windows for DEXA:

Scheduled Visit Number	Time Interval (label on output)	Time Interval (Day) ^a	Target Time Point
1, 2	Baseline	-35 to 30	1
6	Month 6	31 to 270	180
8	Month 12	>=271	360

^a The randomization day is Day 1.

The analysis windows for Pharmacokinetics is given in [Table 9](#).

Table 9: Definition of windows for Pharmacokinetics

Scheduled Visit Number	Time Interval (label on output)	Time Interval (Day) ^a	Target Time Point
3	Month 1	2 to 45	30
5	Month 3	46 to 135	90
6	Month 6	136 to 270	180
8	Month 12	>=271	360

^a: The randomization day is Day 1

Baseline is defined as the last non-missing observation (including an unscheduled visit) prior to or equal to Day 1 (except for DEXA and Bone age, where baseline includes up to 30 days and 180 days post-baseline, respectively).

For post baseline observations, if more than one visit (including an unscheduled visit) occurs in the same time window, the visit nearest to the target day will be used in the analysis. In the case of an equal distance in time, the latest visit will be used.

Data that are not used in the analysis due to multiple observations or being excluded from the above defined time intervals will be displayed in the data listing.

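### SAP Table 8 analyses early-withdrawal DEXA scans from Day 31 onward as Month 6 changes; the SAP needs a narrower-window sensitivity analysis and separate reporting of those scans

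*Protocol*

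**What the plan says.** SAP Section 3.1, Table 8, sets three DEXA windows: baseline from Day -35 to Day 30, Month 6 from Day 31 to Day 270 (target Day 180), and Month 12 from Day 271. The late baseline limit is deliberate. The general rule stops baseline at Day 1, "except for DEXA and Bone age, where baseline includes up to 30 days and 180 days post-baseline, respectively". When one window holds several post-baseline visits, "the visit nearest to the target day will be used in the analysis".

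On the protocol side, Section 9.3 states: "DEXA scans (without sedation) will be obtained at baseline, Month 6, and Month 12/early withdrawal". Section 10.2 adds: "If a subject discontinues treatment before the end of the open-label treatment phase, the end-of-study assessments should be obtained". An early-withdrawal scan can therefore fall on any study day, and Table 8 labels it by that day.

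The sentence on repeat-scan intervals, "The ISCD suggests a minimum monitoring time interval of 6 months for repeating BMD measurement", stands in Protocol Section 16.1 in a list introduced by "A 1-year study duration is justified based on the following".

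SAP Section 7.4 summarises BMD and BMC by visit, counts Z-score decreases of more than 0.5, 1.0 and 2.0, and adds an MMRM. The example code in Section 7 requests treatment least-squares means without a visit term, so the contrast is averaged over the post-baseline visits.

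**The concern.** A child who withdraws between Day 31 and the Month 6 visit has one post-baseline scan. The nearest-to-target rule has nothing to choose between, so that scan becomes the Month 6 value. Day 31 lies inside the 6- to 8-week titration period, and a scan on Days 31 to 90 is closer to Day 1 than to Day 180. If the baseline scan was late, the interval shrinks further: a Day 28 baseline and a Day 40 withdrawal scan give a 12-day change reported as Month 6. SAP Amendment 2 widened the baseline window for 4 subjects with late scans. The documents do not say whether any of them withdrew early.

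Bone mineralization is part of the primary objective. Short-interval changes labelled as 6-month changes make the Month 6 means hard to interpret. They also enter the visit-averaged MMRM contrast, where Month 6 is one of only two post-baseline DEXA visits. If the effect builds up with exposure, they shrink the observed difference in a study designed to look for harm.

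**Working it through.** **Inputs.** One-year dropout is 29%, taken from reference-study rates of 22% and 35% (Protocol Section 11.2). There are 141 children per arm, of whom 100 complete. The Month 6 visit is Day 180 ± 7, so the earliest on-schedule scan is Day 173. The windows are those of SAP Table 8. Dropout timing, the share of leavers scanned and the time course of the effect are not in the documents and are assumed.

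**The plan's own figures.** 100 / (1 − 0.29) = 140.8, rounded up to 141: reproduced. BMD Z-score half-width: 1.96 × 0.4 × √(2/100) = 0.111. The stated 0.12 matches if rounded up.

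**Leavers whose only post-baseline scan is labelled Month 6.** With a constant hazard, S(d) = exp(−λd/360) and λ = −ln(0.71) = 0.3425.

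- Leaving on Days 31 to 172: S(30) − S(172) = 0.972 − 0.849 = 0.123, or 17.3 of 141 per arm, at mean Day 100.
- Reaching Day 173: 0.849, or 119.7 per arm.
- Share of Month 6 values: 17.3 / (17.3 + 119.7) = 12.6%.

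**Dilution if the effect is proportional to days on drug.** 0.126 × (1 − 100/180) = 0.056, so the Month 6 difference keeps about 94% of its Day 180 size. Counting only scans before Day 136: S(31) − S(136) = 0.092, or 13.0 per arm; the share is 9.5% at mean Day 82.6, and 0.095 × (1 − 82.6/180) = 0.051.

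**Dilution if the effect follows cumulative dose.** On the topiramate schedule for ages 10 to 15, the dose through Day 31 is 7 × (50 + 100 + 150 + 200) + 3 × 300 = 4,400 mg. Through Day 180 it is 3,500 + 7 × 300 + 145 × 400 = 63,600 mg. A Day 31 scan then reflects 6.9% of the Day 180 exposure, against 31/180 = 17% by time. The dilution becomes 6.4%.

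**Range.**

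| Scenario | Understatement at Month 6 |
|---|---|
| 22% dropout, constant hazard, half of leavers scanned, time scale | 2.2% |
| 29%, constant hazard, all scanned, time scale | 5.6% |
| 29%, constant hazard, all scanned, dose scale | 6.4% |
| 35%, front-loaded hazard (Weibull shape 0.5), all scanned, dose scale | 9.0% |
| All 29% leave evenly over Days 31 to 172 | 13 to 14% |
| All 29% leave on Day 31 | 24 to 27% |

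The last two rows are outer bounds and not expectations.

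**Visit-averaged contrast.** On the linear time scale, set the effect at 0.5 for Day 180 and 1 for Day 360, with Month 12 undiluted. The average is (0.5 + 1)/2 = 0.75. With Month 6 diluted by 5.6% it is (0.472 + 1)/2 = 0.736, about 2% lower.

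**With Month 6 opening at Day 136.** Only leavers on Days 136 to 172 remain: about 4.3 per arm, with a dilution of about 0.5% (0.1 to 0.7% over the same dropout and scanning range).

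**The case against.** Much of the opposing case stands.

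- A reader might infer that the protocol sets a 6-month minimum between scans and that Table 8 breaks it. It does not. The Section 16.1 sentence supports the study length, and the protocol itself calls for a scan at early withdrawal whenever that falls. The sentence bears only on how far a change over a few weeks can be read as a bone result.
- A reader might also infer that Table 8 departs from the SAP's own convention, because Tables 2, 4, 5, 7 and 9 open Month 6 at Day 136. Those tables have a Month 3 window ending on Day 135, and DEXA has no Month 3 visit. The like-for-like Table 3 (renal ultrasound, Cogstate, Tanner staging, 24-hour urine) runs from Day 2 to Day 270. Day 136 is therefore a borrowed bound. It is still about 4.5 months, and only 106 days after a Day 30 baseline.
- Not every scan from Day 31 counts as Month 6. The window closes at Day 270, and an early scan is used only if the child has none nearer Day 180.
- Dropping leavers' only on-treatment scan is itself a selection, since some may have left for safety reasons. This argues for a sensitivity analysis over simple exclusion.
- Dilution of the decrease percentages looks plausible but does not follow. SAP Section 3 divides, in general, by the analysis population, so an early scan can add to the numerator but cannot enlarge the denominator.
- The effect is small. A Month 6 difference of 0.11 Z-score units would shrink by about 0.11 × 0.056 = 0.006. The interim BMD endpoint was Month 12, the SAP calls the MMRM a sensitivity analysis, and no formal testing is planned.

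None of this removes the mislabelling for a child whose single post-baseline scan comes weeks after baseline.

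**Conclusion.** The point holds as a labelling weakness of modest size. Under 29% dropout at a constant hazard, with all leavers scanned, equal dropout in the arms and an effect that grows with exposure, the Month 6 mean difference is understated by about 5 to 6%, and by about 2 to 9% over the stated dropout range. A smaller share carries into the visit-averaged contrast. Enrolment stopped early, so actual counts will be below the 17 per arm computed from 141.

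The stronger reading, that Table 8 biases the bone result toward no harm, is not established. The documents give no time course for BMD, and the protocol's introduction says that acidosis, the suspected mechanism, generally arises early in treatment. If leavers lose bone faster, or if dropout differs by arm, the bias could run either way. A child whose only scan falls between Day 181 and Day 270 has more exposure than the label implies. Some pull on the Month 12 estimate through the model covariance is possible, but nothing in the documents allows it to be sized.

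**What to change.** In SAP Sections 3.1 and 7.4:

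- Prespecify a sensitivity analysis of the Month 6 DEXA summaries and the DEXA MMRM with Month 6 defined as Days 136 to 270, the bounds already used in Tables 5 and 9. It leaves no gap before Month 12 at Day 271. Alternatively, make this the main window and keep Days 31 to 270 as the sensitivity analysis.
- Tabulate and list scans on Days 31 to 135 separately as early-withdrawal scans, with the actual number of days since the baseline scan.
- Keep these scans in the counts of Z-score decreases of more than 0.5, 1.0 and 2.0.

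The cost is one extra run of existing programs and one added table and listing. The downside is that a few leavers' only post-baseline scan is absent from the narrower-window analysis, which is why both windows should be shown.

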16.2. Regulatory Ethics Compliance

16.2.1. Investigator Responsibilities

The investigator is responsible for ensuring that the clinical study is performed in accordance with the protocol, current ICH guidelines on Good Clinical Practice (GCP), and applicable regulatory and country-specific requirements.

Good Clinical Practice is an international ethical and scientific quality standard for designing, conducting, recording, and reporting studies that involve the participation of human subjects. Compliance with this standard provides public assurance that the rights, safety, and well-being of study subjects are protected, consistent with the principles that originated in the Declaration of Helsinki, and that the clinical study data are credible.

16.2.2. Independent Ethics Committee or Institutional Review Board

Before the start of the study, the investigator (or sponsor where required) will provide the IEC/IRB with current and complete copies of the following documents:

- Final protocol and, if applicable, amendments
- Sponsor-approved informed consent form and assent forms (and any other written materials to be provided to the subjects)
- Investigator's Brochure (or equivalent information) and amendments/addenda
- Sponsor-approved subject recruiting materials
- Information on compensation for study-related injuries or payment to subjects for participation in the study, if applicable

- Investigator's curriculum vitae or equivalent information (unless not required, as documented by the IEC/IRB)
- Information regarding funding, name of the sponsor, institutional affiliations, other potential conflicts of interest, and incentives for subjects
- Any other documents that the IEC/IRB requests to fulfill its obligation

This study will be undertaken only after the IEC/IRB has given full approval of the final protocol, amendments (if any), the informed consent form, assent forms, applicable recruiting materials, and subject compensation programs, and the sponsor has received a copy of this approval. This approval letter must be dated and must clearly identify the IEC/IRB and the documents being approved.

During the study the investigator (or sponsor where required) will send the following documents and updates to the IEC/IRB for their review and approval, where appropriate:

- Protocol amendments
- Revision(s) to informed consent form, assent forms, and any other written materials to be provided to subjects
- If applicable, new or revised subject recruiting materials approved by the sponsor
- Revisions to compensation for study-related injuries or payment to subjects for participation in the study, if applicable
- New edition(s) of the Investigator's Brochure and amendments/addenda
- Summaries of the status of the study at intervals stipulated in guidelines of the IEC/IRB (at least annually)
- Reports of adverse events that are serious, unlisted/unexpected, and associated with the investigational drug
- New information that may adversely affect the safety of the subjects or the conduct of the study
- Deviations from or changes to the protocol to eliminate immediate hazards to the subjects
- Report of deaths of subjects under the investigator's care
- Notification if a new investigator is responsible for the study at the site
- Annual Safety Report and Line Listings, where applicable
- Any other requirements of the IEC/IRB

For all protocol amendments (excluding the ones that are purely administrative, with no consequences for subjects, data, or study conduct), the amendment and applicable informed consent/assent form revisions must be submitted promptly to the IEC/IRB for review and approval before implementation of the change(s).

At least once a year, the IEC/IRB will be asked to review and reapprove this clinical study. The reapproval should be documented in writing (excluding the ones that are purely administrative, with no consequences for subjects, data, or study conduct).

At the end of the study, the investigator (or sponsor where required) will notify the IEC/IRB about the study completion.

16.2.3. Informed Consent

Parents (or a legally acceptable representative) and pediatric subjects must give written consent and assent, respectively, according to local requirements, after the nature of the study has been fully explained. Assent must be obtained from children (minors) capable of understanding the nature of the study, typically subjects 7 years of age and older, depending on the institutional policies, as described below. The consent and assent forms must be signed before performance of any study-related activity. The consent form and assent forms that are used must be approved by both the sponsor and by the reviewing IEC/IRB and be in a language that the parents or legally acceptable representative and subject can read and understand. The informed consent and assent should be in accordance with principles that originated in the Declaration of Helsinki, current ICH and GCP guidelines, applicable regulatory requirements, and sponsor policy.

Before enrollment in the study, the investigator or an authorized member of the investigational staff must explain to potential subjects and their parents or legally acceptable representatives the aims, methods, reasonably anticipated benefits, and potential hazards of the study, and any discomfort participation in the study may entail. Subjects will be informed that their participation is voluntary and that they may withdraw consent to participate at any time. They will be informed that choosing not to participate will not affect the care the subject will receive for the treatment of his or her disease. Subjects will be told that alternative treatments are available if they refuse to take part and that such refusal will not prejudice future treatment. Finally, they will be told that the investigator will maintain a subject identification register for the purposes of long-term follow-up if needed and that their records may be accessed by health authorities and authorized sponsor staff without violating the confidentiality of the subject, to the extent permitted by the applicable law(s) or regulations. By signing the informed consent and assent forms the subject and parents or legally acceptable representative is authorizing such access, and agrees to allow his or her study physician to recontact the subject for the purpose of obtaining consent and assent for additional safety evaluations, if needed.

The subject and parents or legally acceptable representative will be given sufficient time to read the informed consent form and the opportunity to ask questions. After this explanation and before entry into the study, consent and assent should be appropriately recorded by means of either the subject's or his or her legally acceptable representative's personally dated signature.

After having obtained the consent, a copy of the informed consent form must be given to the subject.

If the subject and parents or legally acceptable representative is unable to read or write, an impartial witness should be present for the entire informed consent process (which includes reading and explaining all written information) and should personally date and sign the informed consent and assent forms after the oral consent of the subject and parents or legally acceptable representative is obtained.

Children (minors) or subjects who are unable to comprehend the information provided can be enrolled only after obtaining consent from parents or a legally acceptable representative. Assent must be obtained from children (minors) capable of understanding the nature of the study, typically subjects 7 years of age and older, depending on the institutional policies. Written assent should be obtained from subjects who are able to write. A separate assent form written in language the subject can understand should be developed for adolescents. After having obtained the assent, a copy of the assent form must be given to the subject, and to the subject's parent and/or legally acceptable representative.

